**Data Analysis:** “Go/No Go” decisions are based on traditional statistical significance (Aim 1) and effect sizes (Aim 2). Formal statistical testing is conducted using linear mixed-effects (LME) models; hypothesis tests are 2-sided ( $\alpha=0.05$ ). Model parameters are estimated via the R lme4 package and Cohen’s  $d$  is estimated via the EMAtools package. Type I errors are minimized by constraining the number of primary analyses; secondary analyses use false discovery rate corrections. Expected attrition rates are described above. Because outcome measures involve a “change from baseline”, baseline metrics are compared between PBO and AMPH arms, and any baseline differences are addressed in the outcome analyses. Differential drop-out rates from PBO vs. AMPH arms are monitored. Data are assumed to be missing at random; full information maximum likelihood estimators are used, and all data/cases are included in analyses. Clinical follow-up is pursued with all patients exiting the study through post-TCT week 12. Cohort differences: For between-subject contrasts (main effect of drug), differences in age, antipsychotic and anticholinergic loads are tested and used as covariates. Sex differences are tested for all measures based on known sex differences in AMPH sensitivity. NIH Data Harmonization: 3 “PhenX Toolkit” (NOT-MH-15-009) measures of function are used; see above and “Resource Sharing Plan”.

**Aim 1 – Confirm target engagement:** The primary dependent measure of target engagement is AMPH-enhanced APS learning. APS learning is defined as the reduction in Sound Sweeps APS threshold (ms) pre- to post-assessment. Target engagement was demonstrated in MH59803, and will be confirmed if APS learning is increased by AMPH either in a within-subject comparison (AMPH group, “Test 2 vs. 1”), or in a between-subject comparison (AMPH group vs. placebo group change “Test 2” vs. “Test 1”) (note that AMPH and PBO groups are matched by Test 1 PBO performance via stratified randomized assignment). Effect sizes and inferential statistics are based on LME models with random intercepts. A statistically significant main effect of drug (PBO vs. AMPH) on APS learning in either within- or between-subject contrasts is a “Go” criteria and confirms target engagement.

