General Statistical Approach: Hypothesis tests are 2-sided ($\alpha=.05$). Type I error is controlled by selecting optimal *a priori* targets for primary analyses; secondary analyses use false discovery rate corrections. When appropriate, missing data are handled via multiple imputation or full information maximum likelihood estimation. Expected drop-out rates and ways to minimize them are described in the parent application.

Differential drop-out rates from PBO vs. AMPH arms are monitored. Clinical follow-up is pursued with all patients exiting the study through post-TCT week 12.

Cohort differences: For between-subject contrasts (drug), baseline demographic, clinical, antipsychotic/anticholinergic load and performance differences are tested and used as covariates if indicated. Sex differences are tested for all measures.

Procedures for Alternative or Unexpected Results: Linear mixed-effects models allow for the analysis of all available data using an intent-to-treat approach. This approach, however, assumes that data are missing at random. A potential concern is nonrandom dropout, particularly when dropout is related to the (missing) outcomes; that is, not missing at random. To make the missing at random assumption more plausible, we will explore the use of auxiliary variables. Auxiliary variables are covariates that predict both dropout and outcomes. By adding auxiliary variables to our models, nonrandom dropout is corrected by conditioning treatment effects on the predictors of dropout.

Primary Efficacy Endpoint(s): Aim 1: Target engagement – APS learning will be significantly greater under AMPH vs. PBO conditions. Aim 2: Pilot trial - Compared to PBO arm patients, AMPH arm patients will exhibit greater clinical benefit, as indicated by one or more of the following: greater, faster or more durable improvements in PANSSt (reduced scores; see below, “Go/No-Go”), MCCBc (increased scores) or WHODAS (reduced scores).

Secondary Efficacy Endpoint(s): Aim 3: Biomarkers - baseline levels of specific neurocognitive or EEG-based measures, or changes in specific measures with initial AMPH exposure, predict greater sensitivity to AMPH-enhanced neurocognitive, clinical or functional gains over 30 sessions of TCT.

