1) Two separate but parallel protocols were approved by the UCSD IRB (protocols #191811, #201502) and posted on ClinicalTrials.gov. Due to the low recruitment numbers, the two parallel studies were combined and placebo groups were pooled, to yield a 3-group design 2) subject randomization changed from 1:1 to a 2:1 active : placebo ratio; and 3) adjustments were made to the planned statistical analyses, appropriate to the reduced sample size.

Based on known benefits of TCT in psychosis patients, no “placebo TCT” condition (e.g., video game) was included, for ethical and pragmatic reasons. Since all subjects received TCT, clinical gains over time in all groups might reflect, to some degree, the benefits of TCT. Pharmacologic augmentation by AMPH would only be evident if/when benefits in “TCT+active drug” groups exceeded those in “TCT+PBO” groups.

The primary goal of this study was to assess the clinical, neurocognitive and functional gains associated with the addition of AMPH to a full course of TCT. In total, there were 3 primary outcome measures and 5 secondary outcome measures. The primary clinical outcome measure was the Positive and Negative Symptom Scale (PANSS) total score; positive and negative subscale scores were secondary outcomes. Because they were highly correlated with total scores ($r=0.92$ at T_1), PANSS general scores are reported but are not outcomes. The primary neurocognitive outcome was the MCCB Composite Score. The primary functional outcome was the World Health Organization Disability Assessment Schedule (WHODAS 2.0, 12-item). Secondary clinical outcome measures also included the Patient Health Questionnaire (PHQ-9), the Young Mania Rating Scale (YMRS) and the Psychotic Symptoms Rating Scale (PSYRATS) hallucinations subscale.

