Clinical, neurocognitive and functional outcome scores were treated as continuous variables and analyzed in three ways. First, they were submitted to linear mixed-effects (LME) models⁵⁹ for both between-group (interaction model: TCT+AMPH vs. TCT+PBO) and within-group (time model: baseline vs. P30, all groups) analyses. LME analyses included data from all randomized subjects (including those who did not complete 30 AT sessions) and modeled random intercepts to account for within-subject dependencies. Second, because sample sizes fell well below target levels, to test the hypothesis that active drugs would augment the impact of a 30-session course of TCT, the effect size (Cohen's d) of the change from baseline to P30 (“difference score”) was calculated for both between-group (TCT+AMPH vs. AT+PBO) and within-group (baseline vs. P30, all groups) comparisons. Between-group effect sizes were calculated as:

$$d = [(drug score T_1 - drug score P30) - (PBO score T_1 - PBO score P30)] / SD_{wav}$$

where SD_{wav} is the weighted average standard deviation. Within-group effect sizes were calculated as:

$$d = (score at T_1 - score at P30) / SD_{av}$$

where SD_{av} is the average of the standard deviations of the T_1 and P30 measures^{60,61}.

Third, to disentangle the salutary contributions of TCT alone vs. TCT+active drug to within-subject effect sizes, a “threshold” for positive active drug effects was set at “*d=0.4 above PBO values*”:

$$d(\text{active drug}) \geq d(\text{PBO}) + 0.4.$$

Because clinical gains from TCT+PBO were expected to be approximately $d=0.4$, this added threshold of “ $d=0.4$ above PBO” for drug-enhanced TCT meant that an estimated combined large effect size (at least $d=0.8$) would be required for a drug effect to be viewed as meaningful. Outcomes using thresholds from $d=0.2$ to $d=0.6$ were reported.

The use of effect size comparisons in addition to p-values is common in clinical trials research as a way to measure effects independent of sample size. It is particularly useful when, as in the current study, sample sizes fall below targets identified based on traditional power analyses. Effect size “thresholds” have been used by others to argue that TCT neurocognitive benefits exceed levels produced via PBO or practice effects (generally $d \approx 0.18$).

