Indirect indicators of clinical impact included subject attrition, C-SSRS responses, treatment satisfaction and adverse events (AEs). AMPH group subjects were evaluated for abnormal involuntary movements (AIMS) and for deleterious effects of AMPH cessation (AMPH Cessation Symptom Assessment). Analyses included non-parametric (Chi-Square) and parametric (rmANOVA) tests.

Linear mixed-effects models for outcome measures included all subjects who were randomized; df were estimated using the Satterthwaite approximation. Between- and within-group effect sizes for clinical, neurocognitive and functional measures were calculated based on all subjects who completed 30 TCT visits and P30 testing (“completers”). For all analyses, α was set at 0.05; for analyses of the 5 secondary outcome measures, findings were also evaluated with a more restrictive alpha level (0.01) to correct for multiple comparisons.

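### The modified AMPH versus pooled-placebo analyses fix no T_1 adjustment, which costs precision, and no analysis addresses the placebo pooling or the allocation change

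*SAP*

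**What the plan says.** The Project Modification section of the SAP reports that "the two parallel studies were combined and placebo groups were pooled, to yield a 3-group design", and that allocation moved from 1:1 to 2:1 active to placebo. The two studies had begun as separate comparisons of AMPH with placebo and of memantine with placebo.

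The AMPH versus placebo contrast is then made in two ways:

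- **Mixed model.** It is a group-by-time interaction model that "modeled random intercepts to account for within-subject dependencies". On the analysis set: "Linear mixed-effects models for outcome measures included all subjects who were randomized".
- **Effect size.** Added "because sample sizes fell well below target levels", Cohen's d "was calculated for both between-group (TCT+AMPH vs. AT+PBO) and within-group (baseline vs. P30, all groups) comparisons". The between-group formula is the raw difference in T_1-to-P30 change divided by SD_wav. These effect sizes "were calculated based on all subjects who completed 30 TCT visits and P30 testing".

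Neither analysis names the T_1 score as a covariate. Two general statements on baseline differences come from the two-arm plan. SAP, Cohort differences: "load and performance differences are tested and used as covariates if indicated". Protocol, Data Analysis: "baseline metrics are compared between PBO and AMPH arms, and any baseline differences are addressed in the outcome analyses". Neither gives a test, a cut-off or a method. The randomisation strata are sex, age and Test 1 APS learning, not baseline PANSS, MCCB or WHODAS.

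No section names a protocol-of-origin term, an allocation-period term or a concurrent-placebo analysis, or gives numbers by protocol and period.

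**The concern.** There are two separate issues.

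**Precision.** The T_1 score of each outcome is already collected. Leaving it out as a fixed covariate discards information in a trial that admits a shortfall in recruitment. It also leaves the estimate open to chance T_1 imbalance, which stratification does not control for these outcomes. If the general covariate statements still apply, the fitted model also depends on what the baseline comparison happens to show.

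**Comparability of the control group.** Placebo patients from the memantine protocol may never have been randomised against AMPH. If the ratio changed during enrolment, AMPH and placebo patients also come from different mixes of calendar time. A reader cannot tell whether the contrast would hold against placebo patients randomised alongside AMPH.

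**Working it through.** **Inputs.** Two-sided alpha is 0.05 (SAP). The correlation r = 0.8 is stated only for Aim 1 target engagement. For PANSS, MCCB and WHODAS, both r = 0.8 and r = 0.5 are assumptions. The Protocol plans N = 27 randomised and n = 18 completing per arm; actual numbers are lower and not stated. T_1 and P30 are each given SD 1.

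**1. The plan's own figure.** For Aim 1, with d = 0.5, 80% power and r = 0.8, the SD of change is sqrt(2(1-0.8)) = 0.632. The two-sample formula gives 26 per group, or 27 with the t distribution. The stated 27 therefore reproduces as a change-score design and is not in error.

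**2. Completer effect size.** Residual variance per patient is 2(1-r) for change and 1-r² after T_1 adjustment.

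| r | Change | Adjusted | Reduction |
|---|---|---|---|
| 0.8 | 0.40 | 0.36 | 10% |
| 0.5 | 1.00 | 0.75 | 25% |

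**3. Planned mixed model.** Suppose only T_1 and P30 are modelled. The per-arm variance of the contrast is (1-r²)/n + (1-r)²/N. With a common T_1 mean across arms (constrained baseline) it is (1-r²)/n.

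- r = 0.8: 0.36/18 + 0.04/27 = 0.02148, against 0.02000, a cut of 6.9%.
- r = 0.5: 0.75/18 + 0.25/27 = 0.05093, against 0.04167, a cut of 18.2%.

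The modified SAP does not say whether the session 10 and 20 visits enter the model. I repeated the calculation by generalised least squares with four visits, equal correlation between visits and 9 of 27 patients per arm lacking P30. The table shows the variance reduction against the planned model.

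| Scenario | Constrained baseline, r = 0.8 / 0.5 | P30 regressed on T_1, completers only, r = 0.8 / 0.5 |
|---|---|---|
| T_1 and P30 only | 6.9% / 18.2% | 6.9% / 18.2% |
| Four visits, dropout spread evenly | 7.3% / 18.7% | 1.4% / 15.7% |
| Four visits, all dropouts reach session 20 | 7.5% / 19.0% | -1.7% / 14.3% |

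The constrained-baseline gain is stable. The gain of a P30 regression over the planned model is not.

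**4. Chance imbalance.** The SD of the T_1 difference between arms is sqrt(2/n). A one-SD imbalance moves the change-score contrast by (1-r) times that.

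- n = 18: sqrt(2/18) = 0.33, so 0.07 SD (r = 0.8) or 0.17 SD (r = 0.5).
- n = 10 (assumed): sqrt(2/10) = 0.45, so 0.09 or 0.22 SD.

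**5. Pooling and ratio change (illustration only).** Let f be the fraction enrolled before the change, with equal enrolment by protocol and AMPH:memantine:placebo at 1:1:1 afterwards. All of these are assumptions.

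- The memantine-protocol share of placebo is (f/4)/(f/2 + (1-f)/3): 0.17, 0.30 and 0.41 at f = 0.25, 0.50 and 0.75. Multiplied by an assumed protocol difference of 0.2-0.5 SD, this gives 0.03-0.20 SD. At f = 0 it is zero.
- The share enrolled before the change is higher in placebo than in AMPH by 0.13, 0.17 and 0.13. Multiplied by an assumed drift of 0.2-0.5 SD, this gives 0.03-0.09 SD.
- If those memantine-protocol patients are excluded, the standard error of the AMPH contrast rises by 4-12%. With s the excluded share and n = 10-18 placebo completers, the standard error of restricted minus pooled is sqrt(2(1-r)[1/(n(1-s)) - 1/n]) = 0.07-0.26 SD. Even at the 0.5 SD difference, the bias is at most about 1.7 of these standard errors (0.20/0.12).

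**The case against.** The strongest reply is that baseline is not ignored. T_1 is a response in the mixed model and is subtracted in d, and both contrasts are unbiased under randomisation. That stands. A reader might infer that the missing covariate biases the AMPH comparison; the documents do not support this.

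A reader might also convert the 10-25% variance cut into a power gain for the completer effect size. That does not hold, because the SAP specifies no test of that d; its named inferential model is the mixed model. Against that model, a simple P30 regression drops randomised patients without P30 and may gain almost nothing at r = 0.8. This also stands, and is why a constrained-baseline model is the better remedy.

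It is fair to ask whether the general covariate statements survive the modification. If they do not, covariate choice is not data-driven and the analyses are simply unadjusted. If they do, adjustment is possible but has no stated rule. T_1 adjustment is not fixed in either case.

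On pooling, the studies were described as parallel and sat under one institution's IRB. No document gives a protocol difference, a drift, a date of change or counts, and 2:1 has more than one reading. A reader might infer that the pooled contrast is biased; nothing here shows that. The restricted estimate is also too imprecise to settle the matter. What remains is that the plan neither reports the relevant counts nor offers any check.

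**Conclusion.** The point holds as a modest, correctable gap. The modified between-group analyses do not fix T_1 as a covariate. The cost is precision: 10% (r = 0.8) to 25% (r = 0.5) of the variance of the completer comparison, and about 7% to 18-19% of the variance of the mixed-model contrast if a third of each arm lacks P30. These figures rest on assumed correlations and dropout patterns.

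The pooling and ratio-change gap is also real, but its consequence is conditional. The bias is zero without a protocol difference or drift, and the ranges under working show only what particular assumptions would imply. It justifies counts and a supportive estimate, not a change of primary comparison. The SAP's within-group rule of 0.4 above placebo is not affected by T_1 adjustment.

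**What to change.** **T_1 adjustment.**

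- Compute the completer between-group d from the T_1-adjusted P30 difference, divided by the same SD_wav, whatever the baseline comparisons show.
- Fit the between-group mixed model on all randomised patients with a common T_1 mean across arms, in place of or beside the planned interaction model.
- Keep sex, age and Test 1 APS learning for a supportive model, since the documents do not show that they predict these outcomes.
- The Project Modification section is in the past tense and already quotes an observed correlation (0.92 at T_1). If outcome results are known, label both analyses post hoc.

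**Pooling and ratio change.**

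- Keep the pooled comparison as primary.
- Report numbers by arm, protocol and allocation period.
- Where numbers allow, add one supportive estimate limited to placebo patients randomised concurrently with AMPH or in the AMPH protocol, with a period term (period by time if T_1 stays in the response). State that it is imprecise and cannot confirm the absence of bias. If the restricted group is too small, report the counts alone.

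**Cost.** About one degree of freedom, minor programming on data already collected, and a supportive estimate with a standard error some 4-12% larger in the scenario above. If results are known, the adjusted analyses carry only post-hoc weight.

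### Both of the SAP's effect-size formulas are baseline minus P30, so on the MCCB composite the printed 0.4 threshold is met only when the drug arm's standardised gain is at least 0.4 below placebo's

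*SAP*

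**What the plan says.** All the formulas are in the SAP under Project Modification: Statistical Analysis Plan.

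- **Scope.** "Clinical, neurocognitive and functional outcome scores were treated as continuous variables and analyzed in three ways". The last paragraph of the section confirms that neurocognition is included: "Between- and within-group effect sizes for clinical, neurocognitive and functional measures were calculated", using completers.
- **Within-group d.** "score at T_1 - score at P30) / SD_{av", "where SD_{av} is the average of the standard deviations of the T_1 and P30 measures". Each arm is thus divided by its own SD.
- **Between-group d.** The numerator is "drug score T_1 - drug score P30) - (PBO score T_1 - PBO score P30", divided by a weighted average SD. The orientation is the same.
- **Threshold.** The cut-off for "positive active drug effects was set at" 0.4 above placebo: d(active drug) ≥ d(PBO) + 0.4. Results for cut-offs from 0.2 to 0.6 are also reported. The SAP expects a placebo-arm clinical gain of about d = 0.4. It concludes that a combined d of at least 0.8 "would be required for a drug effect to be viewed as meaningful".
- **Direction of benefit.** The SAP's Primary Efficacy Endpoint(s) paragraph counts lower PANSS total and WHODAS scores as improvement, and higher MCCB composite scores. The Project Modification section keeps the MCCB composite as one of three primary outcomes.

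Neither document gives a sign reversal, an absolute value or a separate formula for MCCB.

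**The concern.** Baseline minus P30 is positive when a score falls. That means improvement on PANSS and WHODAS but deterioration on MCCB. For a d that is only reported, the sign would be a matter of presentation. The threshold, however, is a signed inequality, so the sign decides who passes.

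The SAP's intent is the reverse of what the printed rule does on MCCB: "Pharmacologic augmentation by AMPH would only be evident if/when benefits in" the active-drug groups exceed those with placebo. At stake is the judgement of whether amphetamine had a meaningful effect on the primary neurocognitive outcome. The SAP adds the effect-size analyses because recruitment fell well short of target, so this judgement carries interpretive weight.

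**Working it through.** **Inputs.** The two formulas, the 0.4 threshold, the 0.2 to 0.6 range and the expected placebo gain of 0.4 come from the SAP's Project Modification section. The directions of benefit come from the SAP's Primary Efficacy Endpoint(s) paragraph. The documents give no expected placebo-arm gain on MCCB, so four values are assumed:

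- 0: no placebo gain;
- 0.18: the SAP's figure for placebo or practice effects;
- 0.39: the protocol's Significance section, the multi-site trial's effect size after 40 h of training (not stated whether it is a within-arm figure);
- 0.40: the SAP's figure for clinical gains.

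**Step 1: the plan's own figure.** 0.4 + 0.4 = 0.8. This reproduces, provided positive d means improvement.

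**Step 2: the rule on MCCB.** Let g = (P30 − T_1)/SD_av, the standardised gain in an arm. The printed d equals −g. With threshold t:

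−g(drug) ≥ −g(PBO) + t, which is g(drug) ≤ g(PBO) − t.

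No assumption about the SDs is needed, because each arm is standardised by its own.

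**Step 3: placebo gain 0.4 on MCCB.** Printed d(PBO) = −0.40, so the pass mark is −0.40 + 0.40 = 0.00.

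| Drug gain (SD) | Printed d(drug) | Between-group d (equal SDs) | Printed rule |
|---|---|---|---|
| 1.2 | −1.20 | −0.80 | not met |
| 0.8 | −0.80 | −0.40 | not met |
| 0.4 | −0.40 | 0.00 | not met |
| 0.1 | −0.10 | +0.30 | not met |
| 0.0 | 0.00 | +0.40 | met |
| −0.1 | +0.10 | +0.50 | met |

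On PANSS with the same placebo improvement of 0.4, a drug improvement of 0.8 gives d = 0.80 and meets the rule, and one of 0.4 or less does not, as intended.

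**Step 4: other placebo gains and thresholds.** The cells in the first three rows give the largest drug gain (SD) that passes as printed. The last row gives the smallest that passes with the sign corrected.

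| Rule | g(PBO) = 0 | 0.18 | 0.39 | 0.40 |
|---|---|---|---|---|
| Printed, t = 0.2 | −0.20 | −0.02 | +0.19 | +0.20 |
| Printed, t = 0.4 | −0.40 | −0.22 | −0.01 | 0.00 |
| Printed, t = 0.6 | −0.60 | −0.42 | −0.21 | −0.20 |
| Corrected, t = 0.4 | 0.40 | 0.58 | 0.79 | 0.80 |

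At the 0.4 threshold, no drug gain above zero passes for any of the four placebo values.

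**Step 5: raw gains.** With similar SDs, a lower standardised gain is also a lower raw gain. If the placebo arm does not decline, a larger raw gain on drug can pass the printed rule only when g(PBO) > t and SD(drug)/SD(PBO) > g(PBO)/(g(PBO) − t). That ratio is 0.8/0.4 = 2.0 for g(PBO) = 0.8 and t = 0.4, and 0.39/0.19 = 2.05 for g(PBO) = 0.39 and t = 0.2. If both arms decline, the condition does not apply. For example, placebo −4 with SD 10 (g = −0.40) and drug −3.9 with SD 4 (g = −0.975) meets the printed rule at t = 0.4, since −0.975 ≤ −0.80, although the drug arm's raw change is slightly better. The result in Step 2 is unaffected.

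**The case against.** The strongest reply is that this is a slip of notation with an unmistakable intent. The SAP states the direction of benefit for each primary outcome, speaks of gains and positive drug effects, and does arithmetic that works only if positive d is improvement. An analyst reading those parts together would reverse the sign for MCCB. The section is also written in the past tense, so rewording it changes no future procedure. A wrong sign could be detected from the means with SEM that the SAP plans to report.

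Most of this stands, and it limits the weight of the point. The intent is clear, and the documents do not show that any result was computed the wrong way. PANSS, WHODAS and the secondary outcomes, which are all symptom scales, are not in question. No threshold is attached to the between-group d.

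It does not remove the error. The formula and inequality are the operative specification, and code that follows them returns the opposite of the stated intent on a primary outcome. A reader of the SAP also cannot tell which sign a reported MCCB d carries.

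**Conclusion.** The concern holds. As printed, the threshold is inverted for the MCCB composite at every cut-off from 0.2 to 0.6. With a placebo gain of 0.4 SD, the pass mark is a drug gain of 0.00 or less instead of 0.80 or more.

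The inversion on standardised gains follows from the formulas alone. The individual pass marks depend on the assumed placebo gain, and the statement about raw gains depends on the arms having similar SDs. The consequence is confined to the third analysis on MCCB and to the sign of the MCCB within- and between-group d. The linear mixed models and the protocol's Go criterion of d of at least 0.5 stand apart from it. It is an error of specification that should be corrected, and it is not evidence that the reported results are wrong.

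**What to change.** Add one sentence to the SAP's Project Modification section: d is coded so that a positive value means improvement for every outcome. That means P30 minus T_1 for the MCCB composite, in both the within-group and between-group formulas, and T_1 minus P30 for PANSS total, WHODAS and the symptom scales. Apply the 0.4 threshold and the 0.2 to 0.6 range to that d. Then check the reported MCCB d values and threshold results against the arm means at T_1 and P30.

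The cost is that sentence and one check of the MCCB output. Data, sample size and models are unchanged.
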